2.3.3 Exploratory Efficacy Endpoints

The exploratory efficacy endpoints include the following:

• Cumulative days and time to discontinuation of supportive bladder care for HC, specifically continuous bladder irrigation and/or nephrostomy tubes.

- Summary of HC-associated signs and symptoms other than bladder pain, including urinary frequency, urinary urgency, constant need to urinate, and nocturia.
- Incidence and time to recurrence of HC, defined as two consecutive Bedi grades ≥2 with macroscopic hematuria (visibly bloody urine) that are at least 2 days apart.
- Incidence and time to recurrence of bladder pain.
- Requiring RBC and/or platelet transfusions and the number of required RBC and/or platelet transfusions (measured in transfusion units/participant).
- Change in renal function as assessed by eGFR. For participants requiring dialysis, number of days on dialysis will be captured.
- Time to resolution of BK viruria. Resolution of viruria will be defined by the lower limits of quantitation of the assay used.
- Viremia and viruria with each target virus (ie, BKV, AdV, CMV, HHV-6, JCV, and/or EBV) over time.
- Length of use of any pain medication(s) (IV, oral, or other), including antispasmodics, anticholinergics, and beta-3-agonists, used for control of lower abdominal/bladder pain.
- Use of immunosuppressive agents, by specific agent during the study.
- Number of hospitalizations, number of ICU stays, and number of days of ICU care for any reason.
- Use of antiviral therapies other than cidofovir with potential activity against at least one target virus by specific agent during the study.
- Overall survival, defined as time to death (from any cause) from the time of randomization in days.
- Incidence of relapse or progression of the primary malignancy.
- Overall quality of life as measured by EQ-5D questionnaires.
- Global impression of hemorrhagic cystitis change.

2.3.4 Safety Endpoints

The safety endpoints include the following:

- Incidence and severity of acute GVHD (for the acute GVHD grading scale, see Appendix E
 of the Protocol)
- Incidence and severity of chronic GVHD (for the chronic GVHD grading scale, see Appendix E of the Protocol)
- Incidence and severity of cytokine release syndrome (CRS) (for the CRS grading scale, see Appendix F of the Protocol)

Safety assessments also include adverse events, vital signs, 12-lead electrocardiograms (ECGs), physical examination findings, and clinical laboratory evaluations (blood chemistry, hematology, and urine).

3 STATISTICAL METHODOLOGY

3.1 General Considerations

3.1.1 Study Day from Randomization

Study day will be calculated from the date of randomization, as analysis day = actual assessment/collection/visit date – randomization date (+1 for dates on or after the randomization date and not for dates before the randomization date). All the efficacy endpoints will be summarized at and post randomization based on the study day from randomization.

3.1.2 Study Day from First Dose

Study day will be calculated from the date of first dose of study drug, as analysis day = actual assessment/collection/visit date – first dose date (+1 for dates on or after the first dose date and not for dates before the first dose date). The day of the first dose of study drug will be Day 1, and the day immediately before and after Day 1 will be Day -1 and Day 2. This is different from the protocol for the scheduled visit day, which defined the day of the first dose and randomization as day 0. All the safety endpoints will be summarized based on the study day from the first dose of study drug.

3.1.3 Analysis Visits

All the visits will be assigned to analysis visits according to the visit windows indicated by analysis windows of this SAP (Appendix A). If two or more visits fall into the same analysis window, the visit closest to the planned visit timepoint will be used. If the distances to the planned visit are equal, the latest one will be used. If multiple assessments occur on the same day, the values will be averaged. For laboratory data, if a retest visit can be identified due to result error (eg, laboratory error or physiologically improbable results) in the original test visit, the retest visit will be used in place of the original test result for that visit.

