6.5.2 Study Drug Preparation, Dispensing, and Administration

Posoleucel and placebo will be supplied in cryovials, which are to be transported from liquid nitrogen storage at the clinical site to the cell-thawing and preparation location in a liquid nitrogen Dewar or other suitable container. Details of the cell thawing, preparation for dosing, and administration to the participant will be provided to clinical sites in a separate Cell Therapy Manual.

Cryovials of PSL and placebo will be removed from liquid nitrogen storage and thawed, and the contents transferred to a syringe prior to infusion as described in detail in the Cell Therapy Manual. Study treatment is to be infused into the participant within 30 minutes of thawing (from completion of thaw to completion of infusion). If the location of the participant is remote from the clinical site's cell storage facility, the thawing of the cryovials and preparation of infusion syringes should be conducted in an appropriate location for cell preparation that is sufficiently close to the participant to ensure that no more than 30 minutes elapse between the completion of thawing and infusion.

Premedication is not required, except for participants with a prior history of reaction to blood products who may receive premedication with diphenhydramine 0.25 to 0.5 mg/kg IV or orally (maximum dose of 25 mg) or a similar antihistamine preferred by the study site and/or acetaminophen (paracetamol) 5 to 10 mg/kg IV or orally (maximum dose of 1000 mg) prior to study treatment administration. Premedication with high-dose systemic corticosteroids (ie, prednisone dose >0.5 mg/kg/day or equivalent) is prohibited.

All infusions of PSL or placebo will be administered IV (via central or peripheral line) over approximately minutes as a slow push.

Participants will be monitored according to institutional standards for the administration of blood products and, at a minimum, according to the following requirements:

- Participants in an outpatient setting must remain in the clinic for ≥1 hour after the end of the infusion.
- Vital signs and pulse oximetry will be monitored at baseline and also after the final flush has been administered according to Appendix A.

All findings must be recorded in the eCRF.

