8.8 Vital Signs

Vital sign measurements will include body temperature, blood pressure, heart rate, and respiration rate. Following the infusions of study treatment on Day 0 and Day 14 (±3 days), vital signs will be monitored after the final flush has been administered (or within 5 minutes thereof), and at 15, 30, 45, and 60 minutes (±5 minutes of each of these time points) after the final flush. At every other study visit, they will be measured after resting for 5 minutes as indicated in Appendix A.

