3.5.4 Vital Signs

Descriptive statistics will be provided for vital signs by treatment group, presented as both actual values and changes from baseline over time. All vital sign data will be listed by participants.

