APPENDIX A: ANALYSIS WINDOWS

Table 1.1 Analysis	Visit Window for	Selected ePRO En	dpoints (Dail	y for First Six Weeks)
--------------------	------------------	------------------	---------------	------------------------

Analysis Visit	Target Analysis Day	Low Analysis Day	High Analysis Day
Day 1/Baseline	1		1
Day 2	2	2	2
Day 42	42	42	42
Week 7	50	43	49
Week 23	162	156	162
Week 24	169	163	

Table 1.2 Analysis Visit Window for Selected ePRO Endpoints (Weekly for First Six Weeks)

Analysis Visit	Target Analysis Day	Low Analysis Day	High Analysis Day
Day 1/Baseline	1		1
Week 1	8	2	8
Week 2	15	9	15
Week 3	22	16	22
Week 4	29	23	29
Week 5	36	30	36
Week 6	43	37	43
Week 7	50	44	50
Week 23	162	156	162
Week 24	169	163	

Table 2. Analysis Visit Window for EQ-5D-Y Proxy Version 1, EQ-5D-Y and EQ-5D-5L

Analysis Visit	Target Analysis Day	Low Analysis Day	High Analysis Day
Day 1/Baseline	1		1
Week 1	8	2	8
Week 2	15	9	15
Week 3	22	16	22
Week 4	29	23	29
Week 5	36	30	36
Week 6	43	37	43
Week 8	57	51	57
Week 12	85	79	85
Week 16	113	107	113
Week 24	169	163	

Table 3. Analysis Visit Window for Viral Load (in Blood and Urine), Vital Signs, Pulse Oximetry, Clinical Chemistry and Hematology

Analysis Visit	Target Analysis Day	Low Analysis Day	High Analysis Day
Day 1/Baseline	1		1
Week 1	8	2	11
Week 2	15	12	18
Week 3	22	19	25

Analysis Visit	Target Analysis Day	Low Analysis Day	High Analysis Day
Week 4	29	26	32
Week 5	36	33	39
Week 6	43	40	63
Week 12	85	64	126
Week 24	169	>126	

Table 4. Analysis Visit Window for 12-Lead ECG and Weight

Analysis Visit	Target Analysis Day	Low Analysis Day	High Analysis Day
Day 1/Baseline	1		1
Week 2	15	2	92
Week 24	169	>92

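### Same-day averaging and a baseline without a pre-dose limit keep the by-arm vital-sign summaries from showing the acute change after infusion

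*SAP*

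**What the plan says.** **Collection.** Protocol 8.8 requires vital signs after each of the two infusions, "after the final flush has been administered (or within 5 minutes thereof), and at 15, 30, 45, and 60 minutes". Protocol 8.13 and Appendix A note 23 add pulse oximetry at the same times. For the pre-dose side, Protocol 6.5.2 states: "Vital signs and pulse oximetry will be monitored at baseline and also after the final flush has been administered". Appendix A note 10 places a pulse-oximetry reading before treatment at both Day 0 and Week 2.

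**Analysis.** SAP 3.1.3 sets the rules for reaching one value per analysis visit: the visit closest to target, then the later one if tied, and for repeats within a day: "If multiple assessments occur on the same day, the values will be averaged". SAP 3.4.1 overrides this for Bedi grades (worst case) and Hemostick scores (highest). There is no override for vital signs. The windows come from Appendix A Table 3, "Analysis Visit Window for Viral Load (in Blood and Urine), Vital Signs, Pulse Oximetry" among other measures, and are defined in days only. SAP 3.5.4 plans descriptive statistics by arm, "presented as both actual values and changes from baseline over time", together with a listing of all vital-sign data. It names no post-infusion time point and no worst value.

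**Baseline.** SAP 3.1.4 takes the last non-missing measurement up to and including Study Day 1. Under SAP 3.1.2, Day 1 for safety is the day of the first dose. Table 3 labels that day Baseline.

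**The concern.** Averaging suits replicate readings taken at one time. It does not suit a timed series whose purpose is to reveal a short-lived change. Protocol 1.5.1 names allergic reaction, decreased oxygenation, arrhythmia and hypertension as possible effects of infusion, and the 15-minute readings are the means of seeing several of these. If the readings are collapsed into one daily mean, the briefest changes are diluted most.

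The first infusion adds a second problem. The dosing day is itself eligible as baseline, so readings taken after the cells are given can become the reference from which all later change is measured.

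What is at stake is the by-arm description of acute tolerability. The placebo is the cryopreservation medium without cells, so the contrast between arms in these readings is the direct measured evidence on what the cells add.

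**Working it through.** The documents give no figure to reproduce. The check is arithmetic on the stated schedule.

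**Inputs**
- Post-infusion readings per infusion: 5 (Protocol 8.8, 8.13; Appendix A note 23).
- Pre-dose readings: 1. This is explicit for pulse oximetry on both infusion days and for vital signs at baseline. For vital signs at Week 2 it is inferred, because Appendix A has a vital-signs row and a separate post-infusion monitoring row at that visit.
- Same-day rule: mean of all values (SAP 3.1.3).
- Week 2 window: SAP Days 12 to 18, with no within-day split (Table 3).

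**Dilution at an infusion visit.** Let a change of size D be present at k of the 5 post-infusion readings, with the others at the pre-dose level. The daily mean differs from the pre-dose value by D × k / (1 + 5) = D × k/6.

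Illustration with assumed values, pre-dose systolic pressure 120 and a fall of 40 mmHg:

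| Abnormal readings (k) | Fraction kept (k/6) | Daily mean | Change shown |
|---|---|---|---|
| 1 | 0.167 | (5×120 + 80)/6 = 113.3 | −6.7 |
| 2 | 0.333 | (4×120 + 2×80)/6 = 106.7 | −13.3 |
| 3 | 0.500 | (3×120 + 3×80)/6 = 100.0 | −20.0 |
| 4 | 0.667 | (2×120 + 4×80)/6 = 93.3 | −26.7 |
| 5 | 0.833 | (120 + 5×80)/6 = 86.7 | −33.3 |

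For oxygen saturation, assume 98% with one reading of 86%: (5×98 + 86)/6 = 96.0, so a 12-point fall shows as 2 points.

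If there were no pre-dose reading that day, the fraction kept would be k/5: 0.20 for one reading and 1.00 for all five. The inferred reading therefore affects the size of the dilution but does not create it.

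**First infusion.** SAP 3.1.4 can be applied to Day 1 in two ways.
- *The Day 1 mean is baseline.* The Day 1 change is then 0 by construction. A later normal value of 120 shows a false rise of 120 − 113.3 = +6.7 (one abnormal reading) to 120 − 86.7 = +33.3 (all five). If the same two-reading fall occurred at both infusions, the Week 2 change from baseline would be 106.7 − 106.7 = 0.
- *The readings stay separate.* The last one, nominally at 60 minutes, is baseline. If pressure has recovered by then, later changes are undistorted. If it is still 80, a later 120 shows as 120 − 80 = +40.

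**After the change proposed below.** Each time point is compared with that infusion's own pre-dose value, so the full D is shown (factor 1.00).

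**The case against.** The strongest reply is that the blending is only one reading of the text. The averaging sentence sits among tie-break rules for choosing a visit value and may have been meant for duplicates. Appendix A of the protocol treats vital signs with pulse oximetry as one procedure and post-infusion monitoring as another. The wording of Table 3 matches the first, so the Week 2 value might come from the routine reading alone. That is possible, but the SAP does not say so. Its authors wrote specific rules for Bedi and Hemostick, and wrote none here. Even on this reading, the post-infusion series would be absent from the summary tables instead of diluted, and the by-arm acute change would still not be shown.

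Four stronger conclusions are tempting, and the documents do not support them:
- *That the SAP averages every same-day value.* Bedi and Hemostick are excepted, and a laboratory retest after an error replaces the original.
- *That infusion reactions vanish from the safety analysis.* Infusion-related events are tabulated by incidence and severity with exact 95% intervals (SAP 3.5.2), vital signs are listed (SAP 3.5.4), and the DSMB receives expedited reports of infusion-related events of special interest of at least Grade 2 within 24 hours of an infusion (SAP 3.6).
- *That these are the only objective acute data.* An ECG is taken within 1 hour after each infusion (Protocol 8.9) and summarized by visit (SAP 3.5.5). With one scheduled recording per infusion, averaging does not touch it, although the SAP 3.1.4 baseline wording also admits the Day 0 post-infusion ECG.
- *That any difference between arms would look close to zero.* A change lasting the whole hour keeps 5/6 of its size at Week 2 when measured from a clean baseline.

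It is also true that no endpoint, hypothesis test or stopping rule uses these means.

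**Conclusion.** The point holds for the descriptive vital-sign and pulse-oximetry summaries. A stated rule, applied as written to scheduled readings, keeps between 1/6 and 5/6 of an acute change at an infusion visit, and least when the change is brief. At the first infusion the baseline definition can remove the Day 1 change altogether and bias later changes in the opposite direction.

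This rests on three assumptions. One pre-dose reading exists on each infusion day (inferred for vital signs at Week 2). The averaging rule applies to scheduled time points, since nothing exempts them. Pulse oximetry is summarized alongside vital signs: Table 3 gives it a window, but SAP 3.5.4 does not name it, so neither its summary nor its listing is actually stated. The mmHg and saturation values are illustrations for one participant, not expected differences between arms.

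The change should be made, because it is cheap and the planned tables otherwise miss the purpose of the series. It does not bear on the efficacy conclusions or on the adverse-event tables.

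**What to change.** - **SAP 3.1.3:** limit averaging to repeat measurements at the same nominal time point.
- **SAP 3.1.4:** define safety baseline as the last non-missing value before the start of the first infusion. For ECG this makes the screening recording the baseline.
- **SAP 3.5.4:** name pulse oximetry alongside vital signs. For each infusion separately, summarize both by arm at pre-infusion, end of flush, and 15, 30, 45 and 60 minutes, as change from that infusion's own pre-infusion value. Add each participant's worst post-infusion value. Use the pre-infusion reading as the Week 2 value in the by-visit table.
- **Check:** confirm that the case report form records a pre-infusion vital-sign reading at Week 2, since the protocol text leaves this to inference.

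The cost is SAP wording and one or two extra descriptive tables. Apart from the Week 2 pre-infusion reading to be confirmed, the data are already scheduled for collection, and neither sites nor participants are asked for anything more.

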3.1.4 Definition of Baseline

Baseline is defined as the last non-missing measurement on or prior to Study Day 1.

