8.9 Electrocardiograms

Standard 12-lead ECGs will be performed as indicated in Appendix A. On Day 0 and Day 14, the ECG should be performed within 1 hour after study treatment administration. A post-infusion ECG should be completed for all infusions of study treatment.

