APPENDIX A: SCHEDULE OF PROCEDURES

		Т	I								I
Study Visit/Week											
Visit Window (Days)	NA	NA	NA	±3	±3	±3	±3	±3	±3	±28	±28
Study Procedures											
Pre-screening informed											
consent/assent	X										
Informed consent/assent		X									
[4]											
I/E criteria	X	X									
Demographics [5]		X									
Medical history		X									
Prior and concomitant											
medications [6]											
Adverse events [7]											→
Complete physical		X		X	X	X	X	X	X	X	X
examination [8]				21.		71	21	21	21.	71	
Height and weight [9]		X	X		X						X
Vital signs and pulse			X	X	X	X	X	X	X	X	X
oximetry [10]			71			- 11	2 .	71	21		71
Clinical outcome		-				See Apper	ndix B				→
assessments [11]			ı	1	1	11	1	1	1	1	1
Documentation of HLA		X									
typing [5,12]		V [14]	X	X	X	X	X	X	X	X	X
Hematology [13]		X [14]									
Clinical chemistry [15]	37	X [14]	X	X	X	X	X	X	X	X	X
Viral loads in urine [15]	X	X [14]	X	X	X	X	X	X	X	X	X
Viral loads in blood [13,			X	X	X	X	X	X	X	X	X
15]		37	V		V						37
Pregnancy test [16]		X	X		X						X
FSH [17]		X								 	

Study Visit/Week	Pre-										
Visit Window (Days)	NA	NA	NA	±3	±3	±3	±3	±3	±3	±28	±28
Study Procedures											
Visual assessment of urine by Bedi grading with urinalysis		X	•	(Day 42	ne, then 3 × 2) or until reline, then 1 :	esolution, t	hen 1 × per	week		Inpatient week [18 apart resolution per v Outpation per week resolution	y 43): s: 2 × per] ≥2 days then 1 × week tents: 1 ×
Visual assessment of urine by Hemostick (outpatients only)			At baselin		ly through				solution	2 × per days ap resolution	week 7 week ≥2 art until then 1 × week
Collection of PBMCs for banking of human genetic DNA and plasma [13, 19]			X	X	X	X	X		X	X	X
Acute GVHD evaluation [20]		X	X	X	X		X		X	X	X
Chronic GVHD evaluation [20]			X							X	X
Randomization [21] Distribution of subject cards			X X								
Study treatment administration [22]			X		X						
Post-infusion monitoring [23]			X		X						
12-Lead ECG		X	X [24]		X [24]						X

- Note: Study visits should occur at the study site. If this is not possible, home health visits may be performed as agreed with the Sponsor.
- 1. Participants may complete an optional Pre-Screening Visit that will be conducted from 14 days prior to the randomization visit to the day of the randomization visit. A separate Pre-Screening consent form is available for this purpose.
- 2. All screening and baseline assessments must be performed prior to study treatment administration.

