- 23. Participants will be monitored closely and must remain in the clinic for ≥1 hour after the end of study treatment administration. Vital signs, including body temperature, blood pressure, heart rate, and respiration rate, as well as pulse oximetry will be measured within 5 minutes after the final flush has been administered, and at 15, 30, 45, and 60 minutes (±5 minutes of each of these time points) after the final flush.
- 24. The ECG is to be performed ≤1 hour after study treatment administration.

AdV = adenovirus; BKV = BK virus; CIBMTR = Center for International Blood and Marrow Transplant Research; CMV = cytomegalovirus; DNA = deoxyribonucleic acid; EBV = Epstein-Barr virus; ECG = electrocardiogram; ePRO = electronic patient-reported outcome; ET = Early Termination; FSH = follicle-stimulating hormone; GVHD = graft versus host disease; HCT = hematopoietic cell transplant; HHV-6 = human herpesvirus 6; HLA = human leukocyte antigen; I/E = inclusion and exclusion; JCV = JC virus; LFT = liver function test; MAGIC = Mount Sinai Acute GVHD International Consortium; NA = not applicable; PBMC = peripheral blood mononuclear cell; VST = virus-specific T cell.

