3.5.5 Electrocardiograms

Electrocardiogram (ECG) data will be summarized by visit and treatment group for each quantitative ECG parameter using descriptive statistics. The changes from baseline to each post-baseline visit will also be summarized. All ECG parameters and details of any abnormalities will be listed by participant.

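### The SAP sets baseline by calendar day, so the ECG taken within 1 hour after the first infusion becomes the reference for ECG change

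*SAP*

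**What the plan says.** SAP 3.1.4 defines baseline for all measurements: "Baseline is defined as the last non-missing measurement on or prior to Study Day 1". SAP 3.1.2 makes the first-dose day Day 1 and adds: "All the safety endpoints will be summarized based on the study day from the first dose of study drug". For assessments on the same day, SAP 3.1.3 says: "If multiple assessments occur on the same day, the values will be averaged".

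On ECG timing, Protocol 8.9 says: "On Day 0 and Day 14, the ECG should be performed within 1 hour after study treatment administration". Note 24 to the schedule in Protocol Appendix A repeats it: "The ECG is to be performed ≤1 hour after study treatment administration". The ECG row of that schedule has four entries: screening, Day 0, Week 2 and Week 24. The Day 0 and Week 2 entries carry note 24. Note 2 to the same schedule says: "All screening and baseline assessments must be performed prior to study treatment administration".

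SAP 3.5.5 plans ECG summaries by visit and treatment group, and adds: "The changes from baseline to each post-baseline visit will also be summarized". The windows are in SAP Appendix A, "Table 4. Analysis Visit Window for 12-Lead ECG and Weight": Day 1/Baseline runs up to Day 1, Week 2 covers Days 2 to 92, and Week 24 starts after Day 92.

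**The concern.** A baseline for a change-from-baseline safety summary should be an untreated value. The SAP definition looks only at the calendar day, and for ECG the last tracing on that day comes after the infusion. The SAP therefore drops the pre-dose condition in note 2 of the protocol schedule.

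At stake is the readability of the ECG change table. The protocol requires a post-infusion ECG for every infusion, and its risk section (1.5.1) lists arrhythmia and hypertension among the possible effects of infusion. If the first of these tracings becomes the reference, the table cannot show a change at the first infusion, and a transient effect would reappear as an opposite change at Week 24. The same wording leaves open how the vital signs monitored after the infusion are treated.

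**Working it through.** The plan states no figure to reproduce. The check applies the SAP rules to the protocol schedule.

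**Which ECG is the baseline?**

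1. Study day = date − first-dose date + 1 on or after first dose (SAP 3.1.2). The protocol's Day 0 ECG has study day 0 + 1 = 1.
2. Eligible under SAP 3.1.4 (study day ≤ 1): the screening ECG and the Day 0 post-infusion ECG.
3. The last of these is the Day 0 post-infusion ECG.
4. Table 4 leads to the same result. Both tracings fall in Day 1/Baseline, and SAP 3.1.3 keeps the one closest to the target, Day 1. The next window opens on Day 2, so the post-infusion tracing has no post-baseline row.
5. SAP 3.5.5 gives no ECG-specific baseline that overrides this.

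**How many change summaries remain?**

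| Baseline rule | Reference ECG | Change summaries | From an untreated value |
|---|---|---|---|
| Last value before first infusion | Screening | 3 (Day 1, Week 2, Week 24) | 3 of 3 |
| SAP as written | Day 0, post-infusion | 2 (Week 2, Week 24) | 0 of 2 |

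**What would a transient shift look like?** Assume a shift d within 1 hour of each infusion, none at screening and none at Week 24. The documents give no d; values of 5, 10 and 20 units were tried. Change = value − baseline.

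| Rule | Baseline | Day 1 | Week 2 | Week 24 |
|---|---|---|---|---|
| Pre-dose | 0 | d − 0 = +d | d − 0 = +d | 0 − 0 = 0 |
| SAP, screening on an earlier day | d | d − d = 0 (no row) | d − d = 0 | 0 − d = −d |
| SAP, screening on the dosing day, values averaged | (0 + d)/2 = d/2 | +d/2 (no row) | d − d/2 = +d/2 | 0 − d/2 = −d/2 |

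For d = 10 the pre-dose rule gives +10, +10, 0. The SAP rule gives 0, 0, −10, or +5, +5, −5 with averaging. The pattern is the same for 5 and 20.

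**Vital signs.** Protocol 6.5.2 provides a baseline measurement. Protocol 8.8 adds five sets after the final flush (at the flush, then 15, 30, 45 and 60 minutes), so Day 1 has 1 + 5 = 6 sets. SAP Appendix A Table 3 ends Day 1/Baseline at Day 1 and starts Week 1 at Day 2, so the five sets have no row of their own. Three readings are possible:

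- Monitoring sets kept apart: the baseline is unaffected (0%).
- All six sets averaged under SAP 3.1.3: a shift seen in k of the five moves the baseline by k/6 of its size, from 1/6 = 17% to 5/6 = 83%.
- Last value taken by clock time: the 60-minute reading is the whole baseline.

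On the second-infusion day, pooling would also mix the monitoring sets into the Week 2 visit value.

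**The case against.** **The intent is clear from the protocol.** Note 2 requires baseline assessments before treatment, and note 3 accepts screening values as baseline if done less than 24 hours before dosing. On this view the SAP wording is merely loose. The intent is plain, but the SAP text gives the opposite result for ECG, and no pre-dose ECG is scheduled on Day 0 to fall back on.

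**The study-day count is not named.** SAP 3.1.4 does not say whether Day 1 runs from randomization (3.1.1) or first dose (3.1.2). If it ran from randomization and dosing came on a later day, the post-infusion ECG would fall outside baseline. However, 3.1.2 assigns the first-dose count to safety data and notes that the protocol puts randomization and first dose on the same day.

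**The vital-sign part is hypothetical.** Protocol 6.5.2 separates baseline from post-flush monitoring, and the schedule lists them in separate rows, so the natural reading keeps them apart. This largely stands. The range from 0% to complete replacement measures the ambiguity and is not an estimate of bias. What remains is a sentence missing from the SAP, because the same-day averaging rule has no exception for these sets.

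**The impact is small.** This stands. ECG is not among the safety endpoints in SAP 2.3.4. Actual values by visit and arm, adverse-event tables (including infusion-related events) and participant listings remain, and the placebo arm follows the same schedule. The placebo arm does not restore the lost contrast, though. If the shifts are d_PSL and d_placebo, the SAP rule turns a true Week 24 difference of 0 into −(d_PSL − d_placebo). It cancels only if the two shifts are equal.

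**Conclusion.** The ECG point holds. As written, the SAP makes a post-infusion tracing the baseline, so the first-infusion change is not summarized and neither remaining change summary is measured from an untreated value. This rests on the first-dose study-day count for safety data and on ECGs being done as scheduled. If the screening ECG falls on the dosing day and same-day values are averaged, half of the baseline is still post-infusion.

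The vital-sign point holds only as an ambiguity: the SAP does not say whether the monitoring sets are pooled.

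The consequence is confined to descriptive ECG and vital-sign change-from-baseline summaries. Day 0 central-laboratory samples are collected before dosing and are unaffected, as are the primary test, alpha and power. The correction should be made because the stated rule gives a wrong table and is cheap to repair.

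**What to change.** - **SAP 3.1.4:** define the safety baseline as the last non-missing measurement before the start of the first infusion, by date and time, and name the study-day count used. For ECG this is normally the screening tracing; say that it may serve even if it is older than the 24 hours in note 3 of the protocol schedule.
- **SAP Appendix A Table 4:** add a Day 1 post-infusion row and report that ECG as the first post-baseline time point.
- **SAP 3.1.3 and Appendix A Table 3:** state that post-infusion vital-sign sets are excluded from the Day 1/Baseline and Week 2 visit values and from same-day averaging. Preferably, give them their own rows by nominal time, as change from the same-day pre-infusion value. This last table is an addition that the ECG correction does not require.
- **Protocol Appendix A:** reconcile note 2 with note 24 for the Day 0 ECG.

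The cost is a few sentences, added window rows and some table programming, with no new data. The drawback is that the screening ECG is further from dosing than a same-day tracing would be.
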